3. TREATMENT OF SUBJECTS

3.1 Investigational treatment

The rehabilitation program consists of physical exercise therapy, psychotherapy and dietary consultation.

3.2 Use of co-intervention

There are no restrictions for participants.

4. INVESTIGATIONAL PRODUCT**4.1 Name and description of investigational product(s)**

Not applicable.

4.2 Summary of findings from non-clinical studies

Not applicable.

4.3 Summary of findings from clinical studies

Not applicable.

4.4 Summary of known and potential risks and benefits

Not applicable.

4.5 Description and justification of route of administration and dosage

Not applicable.

4.6 Dosages, dosage modifications and method of administration

Not applicable.

4.7 Preparation and labelling of Investigational Medicinal Product

Not applicable.

4.8 Drug accountability

Not applicable.

5. NON-INVESTIGATIONAL PRODUCT**5.1 Name and description of non-investigational product(s)**

Not applicable.

5.2 Summary of findings from non-clinical studies

Not applicable.

5.3 Summary of findings from clinical studies

Not applicable.

5.4 Summary of known and potential risks and benefits

Not applicable.

5.5 Description and justification of route of administration and dosage

Not applicable.

5.6 Dosages, dosage modifications and method of administration

Not applicable.

5.7 Preparation and labelling of Non Investigational Medicinal Product

Not applicable.

5.8 Drug accountability

Not applicable.

6. METHODS

6.1 Study parameters/endpoints

6.1.1 Main study parameter/endpoint

MFI-General Fatigue assessed 12 months after surgery will be used as the primary outcome. Symptoms of fatigue are assessed using the Multidimensional Fatigue Inventory (MFI) (16). This 20-item questionnaire includes the following five scales: general fatigue, physical fatigue, reduced activity, reduced motivation, and mental fatigue. One can score each question with 1 to 5 points, with sub scores for the five dimensions ranging from 4 to 20. Higher scores indicate increased fatigue.

6.1.2 Secondary study parameters/endpoints

Secondary outcomes are fatigue, frailty, anxiety, depression, quality of life, amount of visceral adipose tissue, skeletal muscle mass and strength, performance status, malnutrition risk and body mass index (BMI) which will be assessed preoperatively, at start and end of the rehabilitation program, and 6 and 12 months after surgery. Furthermore, overall survival will be assessed.

Frailty and anxiety and depression assessment

Frailty will be assessed using the Groningen Frailty Indicator (GFI) (38). The GFI has been developed as a simple screening instrument for frailty. It screens on physical, cognitive, social, and emotional items. The maximum score is 15 points. Patients scoring 5 or more points are considered frail. Anxiety and depression mood will be measured using the Hospital Anxiety and Depression Scale (HADS), consisting of the anxiety (HADS-A) and depression (HADS-D) subscales. Both subscales have a score ranging from 0 to 21 with higher scores indicating more anxiety and depression (39).

Quality of life

The (health-related) quality of life will be assessed using the EORTC-Quality of Life-C30 questionnaire (version 3). The Dutch version of this questionnaire is validated (40).

Body composition measurements

All patients will undergo computed tomography (CT) examinations preoperatively (within 4 weeks preoperative), at baseline (2 weeks after discharge), 17 weeks after discharge and 3, 6 and 12 months hereafter. All examinations are part of standard care and financially covered by the patients' healthcare insurance. The cross-sectional skeletal muscle area (cm²) will be measured on the level of the third lumbar vertebra (L3). This area will be adjusted for patients' height, resulting in the L3 muscle index (cm²/m²). This measure is strongly correlated with total body skeletal muscle mass and this measure is known for its highly reliability and great reproducibility (11, 41). Finally, the amount of visceral adipose tissue will be measured (42). Researchers assessing these two measures will be blinded with regard to whether the patient was part of the treatment group.

Nutritional risk

To assess the nutritional status and the risk of malnutrition all patients are asked to fill in the Patient-Generated Subjective Global Assessment Short Form (PG-SGA SF) (43).

Muscle strength

Muscle strength is a predictor for survival in patients of average and higher age. Furthermore, muscle strength of the extremities are important characteristics of functional performance in elderly (44). Muscle weakness results in decreased self-management and a higher rate of dependency. The strength of the quadriceps muscle will be measured using a handheld dynamometer (MicroFET2). The peak force during contraction will be measured for 5 consecutive seconds (44). A JAMAR® hand dynamometer will be used to measure muscle strength of the upper extremities (45); sitting on a chair with the shoulders adducted and neutrally rotated, the arm in vertical (next to the body) position and the wrist in neutral position, the subject is instructed to squeeze the grip with maximum strength. Decreased strength is defined as <85% of the population-based value, according to Webb and colleagues (46). These sex- and age specific cut-off values are routinely being used in physiotherapist practices in the Netherlands.

Accelerometer data

To objectively assess the duration and intensity and distribution of physical activities and sedentary behaviour all patients are asked to wear an accelerometer on their wrist for seven consecutive days. Measurements will be in accordance with the schedule of the other measurements.

General physical performance

The performance status of patients during daily activities will be investigated using the Karnofsky performance scale. This is a scale ranging from 0 (dead) until 100 (normal general performance without complaints). An in- or decrease of 10 points will be used to detect significant differences. Furthermore, a timed sit-up-and-go test will be performed (47).

Body height and weight

Body height and weight will be measured on the described time points and body mass index (BMI) will be calculated.

Overall and disease-free survival

The possible effect of the intervention on overall and disease-free survival will be assessed on various time points (1, 3, and 5-years) after the intervention. Survival status will be extracted from the municipal registration system or the electronic patient file.

6.1.3 Other study parameters (if applicable)

Baseline parameters: gender, date of birth, weight, length, smoker status, level of education, marital status, ECOG status, est. weight loss last 6 months, comorbidities, diagnosis, TNM stage, tumor grade. date of surgery, surgery type, ASA classification, est. blood loss, radical resection, nr. nodes inspected, nr. nodes positive, hospital length of stay, Clavien-Dindo Classification and the Comprehensive Complications Index.

6.2 Randomisation, blinding and treatment allocation

Patients will be included on the preoperative surgical outpatient department. If at hospital discharge patients score ≥ 4 on the fatigue NRS , they will randomly be assigned to the treatment (rehabilitation program) or control (standard care) group in a 1:1 ratio.

Centralized stratified permuted block randomization will be performed by the Clinical Trial Center using the online ALEA software. The sample will be stratified based on organ (liver, pancreas, biliary tract) and organisation (EMC, LUMC, AMC, UMCG). Block randomisation within each stratum will be performed using variable block sizes ranging from 2 to 4. Neither patients nor therapists will be blinded for the treatment group. All therapists will be blinded for the NRS fatigue score that will be obtained before the start of the rehabilitation program.

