6.3 Study procedures

The intervention will be offered close to the patients home. Patients in the control arm are offered standard medical care according to the local protocols.

- ***Dietary Intake***

At discharge all patients will visit a dietary professional to assess their protein and caloric intake.

- ***Physical exercise therapy***

The physical exercise therapy program will start four weeks after hospital discharge for duration of 12 weeks. The intervention group is offered a supervised and personalized exercise program that is aimed at both cardiorespiratory fitness (aerobic training) and muscle strength (resistance training) (48), which is also considered feasible in patients receiving chemotherapy (30). The program is developed in a close collaboration between physiotherapists, exercise physiologists, revalidation specialists, and medical and surgical oncologists. For each patient, an intake or baseline exercise measurement (i.e. 6 minute walk test and muscle function tests) will be performed at their medical center. Subsequently, the program will be specified to each patient's personal preferences and physical fitness with their physiotherapists. Hereafter, patients will train twice a week for one hour under supervision of a physical therapist. Patients are offered the following program: muscle strength training for 30 minutes per session. One training session exists of a minimum of six exercises: 1. Vertical row (longissimus, biceps brachii, and rhomboideus); 2. Leg press (quadriceps, glutei, gastrocnemius); 3. Bench press (pectoralis major, triceps); 4. Pull over (pectoralis, triceps brachii, deltoideus,

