9.2 Recruitment and consent

Patients will be included on the preoperative surgical outpatient department and with hospital discharge patients will be asked to give written informed consent. Randomization will then be performed.

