- Source Document Verification (SDV) steekproef: 1-10%; wordt uitgevoerd op basis van een van tevoren gedefinieerde lijst van variabelen - inclusief primair eindpunt - die in duidelijke relatie staan tot de veiligheid en geldigheid van het onderzoek.

Patiëntveiligheid (indien van toepassing)

- Controle (Serious) Adverse Event [(S)AE] reporting: steekproef 1-10 % van de proefpersonen.

Studiemedicatie of onderzoeksproduct (indien van toepassing)

- Controle welke instructies deelnemers meekrijgen m.b.t. studiemedicatie of onderzoeksproduct.

Studieprocedures

- Controle of instructies voor uitvoer van studieprocedures aanwezig zijn.

Laboratorium, apotheek en biologische monsters (indien van toepassing)

- Controle of laboratoria GLP gecertificeerd zijn.
- Controle of apotheken GMP gecertificeerd zijn.
- Controle verzameling, labelen en opslag van biologische monsters.

AANDACHTSPUNTEN

- kwalificaties monitor
- terugkoppeling en follow-up van bevindingen van de monitor
 - Termijn van beschikbaarheid monitoring-rapporten.
 - Acties naar aanleiding van verbeterpunten in monitoring rapport: binnen Erasmus MC en in andere deelnemende centra (in geval van multi center trial).

[figure not shown]
- **bewaren van studiegegevens**
 - Gebruik van een adequaat Clinical Data Management Systeem (CDMS).
 - Correct bewaren van ruwe gegevens, gecorrigeerde gegevens en back-ups.
 - Beschikbaarheid van een audit trail (herleidbaarheid van studiedata en aanpassingen).

MONITORINGRAPPORTEN EN BEWAARTERMIJN

Van elke monitoringvisit wordt een schriftelijk verslag gemaakt, het monitoringrapport. Het afdelingshoofd van de hoofdonderzoeker is verantwoordelijk voor de archivering van de monitoringrapporten gedurende minimaal 15 jaar na afronding van het onderzoek. De monitoringrapporten en overige onderzoeksdocumenten zijn op verzoek toegankelijk voor de Raad van Bestuur van het Erasmus MC, en voor door de Raad van Bestuur geautoriseerde.

APPENDIX 2

Overzicht metingen

Event	Timeframe	screening (T0.1)	surgery	Discharge (T0.2)	2 weeks after discharge (T1)	10 weeks after discharge (T1.5)	17 weeks after discharge (T2)	6 months after discharge (T3)	12 months after discharge (T4)
Patient informed consent		x							
Assessment inclusion/exclusion criteria		x							
Registration baseline characteristics		x							
Registration surgical outcomes			x						
Registration recovery				x					
Height		x							
Weight		x			x		x	x	x
Karnofsky performance score		x			x		x	x	x

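### The two-week visit (T1), called baseline for CT and holding the first 6-minute walk, follows open-label randomisation; the only MFI before allocation is preoperative, and the adjusted analysis uses no pre-randomisation fatigue score

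*Protocol*

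**What the plan says.** **Randomisation.** Protocol Section 6.2 ties allocation to the eligibility screen: "If at hospital discharge patients score ≥ 4 on the fatigue NRS", then "they will randomly be assigned to the treatment (rehabilitation program) or control (standard care) group in a 1:1 ratio". Section 9.2 gives the same order, with consent at discharge followed by "Randomization will then be performed".

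**Blinding.** Section 6.2: "Neither patients nor therapists will be blinded for the treatment group". Section 6.1.2 blinds only the researchers who read muscle mass and visceral fat from CT.

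**The label.** Section 6.1.2 schedules a CT "at baseline (2 weeks after discharge". Section 6.3 says that "an intake or baseline exercise measurement (i.e. 6 minute walk test and muscle function tests) will be performed at their medical center".

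**The schedule (Appendix 2).** The MFI is taken at T0.1 (screening, before surgery), T1 (2 weeks after discharge), T2, T3 and T4, but not at discharge (T0.2). The 6-minute walk is taken at T1 and T2 only. The accelerometer is first worn at T1. The exercise programme starts four weeks after discharge (Section 6.3).

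**The analysis.** Section 8 adjusts for gender, age, education, marital status, disease stage and radicality of resection. Section 8.1 compares the 12-month MFI-General Fatigue score with a Mann-Whitney U test. Section 8.2 uses a linear mixed model for longitudinal outcomes.

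**Consent.** Section 9.2: "with hospital discharge patients will be asked to give written informed consent". In Appendix 2 the row "Patient informed consent" is marked at screening, T0.1.

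**The concern.** A baseline value is useful because allocation cannot have influenced it. T1 lacks that protection: patients can know their arm for two weeks before they complete the MFI, quality-of-life, frailty and anxiety/depression forms and perform effort-dependent tests. Hope in one arm, disappointment in the other, a change in behaviour or unequal attendance could separate the arms at T1 before any training has begun.

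The protocol's wording makes T1 an easy choice as the reference point. For the 6-minute walk and the accelerometer it is the only pre-programme measurement. For the MFI an earlier value exists, but it predates surgery, whereas patients enter the randomised comparison because of their fatigue at discharge. No MFI describes them between operation and allocation, and no later analysis document can recover a form that was never completed.

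At stake are the interpretation of the secondary longitudinal and change results, and the precision of the adjusted analysis, which names no fatigue score measured before randomisation.

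**Working it through.** **1. Order of events**

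| Event | Time | Source | Relative to allocation |
|---|---|---|---|
| MFI, grip, quadriceps and other forms, T0.1 | before surgery | Appendix 2 | before |
| Fatigue NRS of at least 4 | discharge | Sections 2.2, 6.2 | before |
| Randomisation, open-label | discharge | Sections 6.2, 9.2 | – |
| T1: CT, MFI, strength, first 6-minute walk, first accelerometer | discharge + 2 weeks | Section 6.1.2, Appendix 2 | after |
| Exercise programme starts | discharge + 4 weeks | Section 6.3 | after |
| T2, T3, T4 | discharge + 17 weeks, 6 and 12 months | Appendix 2 | after |

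T1 therefore lies 2 weeks after allocation and 4 − 2 = 2 weeks before the programme.

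**2. Does T1 enter a stated analysis?**
- Primary test (Section 8.1): 12-month score only, no covariate. T1 plays no part.
- Adjusted analysis (Section 8): six named covariates, none of them a T1 measurement and none a fatigue score.
- Mixed model (Section 8.2): whether T1 is a covariate, the reference or an outcome time point is not stated.

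**3. What would follow if T1 were used as baseline**

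The plan gives no figure for this point. Its target of d = 0.50 sets only the scale; the two-sample t-test returns 63.77 per group for it, which is the plan's 64.

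Work in SD units. Let the 12-month effect on fatigue be −0.50, let the intervention arm score lower at T1 by s solely through knowledge of allocation, and let ρ be the within-arm correlation of T1 with the 12-month score.

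- Adjusting for T1: expected estimate = −0.50 + ρ·s.
- Change from T1: expected estimate = −0.50 + s.
- T1 as an ordinary post-randomisation time point: the 12-month contrast stays at −0.50.

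If s = 0, all three agree and there is no bias. If s is positive, the first two move toward the null; if s is negative, away from it. A simulation of the first formula with 64 per arm agreed with it (for example ρ = 0.5, s = 0.2: formula −0.40, simulated −0.397).

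The documents give neither ρ nor s. For assumed s of 0.1 to 0.3 and ρ of 0.3 to 0.7, the product runs from 0.3 × 0.1 = 0.03 to 0.7 × 0.3 = 0.21 SD. That range reflects only the assumed inputs, in an analysis the protocol does not contain. It is not an estimate for this trial.

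**4. Consent**

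Section 9.2 puts written consent at discharge; Appendix 2 puts it at T0.1. T0.1 also carries the MFI, EQ-5D-5L, QLQ-C30, GFI, HADS and PG-SGA SF and the grip and quadriceps tests. Section 6.1.2 describes the CT examinations as standard care and says no such thing of these measurements. Under Section 9.2 they would precede written consent; under Appendix 2 they need not.

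**The case against.** The strongest reply is that the harm belongs to analyses the protocol does not plan. A reader might infer from Section 8's remark about correcting baseline differences that T1 values will be adjusted for. The named covariates show otherwise. A reader might also infer that the 12-month treatment effect would be biased by a quotable share of the 0.50 target. That is unsupported: the primary test does not use T1, T1 precedes the exercise programme, and any bias needs both an allocation-driven shift and an analysis anchored on T1. This part of the reply stands in full.

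The label is also narrow. Only the CT is explicitly called baseline at two weeks, and its readers are blinded. The baseline exercise measurement in Section 6.3 serves to tailor the programme. The T1 MFI is never called baseline, and Appendix 2 registers baseline characteristics at screening. This too stands, and it limits the point to secondary analyses.

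How T1 enters the mixed model may be settled in a statistical analysis plan that is not shown, so its absence from the protocol is not itself a fault. The visit schedule, however, is fixed in the protocol. No analysis plan can supply an MFI between surgery and allocation, or a walk test before allocation.

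Finally, one might conclude that randomisation should move to T1. The documents do not require it. Randomising at discharge follows directly on the eligibility screen, and the move would cut the time for arranging local therapy from four weeks to two. Nor does a missed T1 visit remove a patient from the primary endpoint.

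**Conclusion.** The point holds in a limited form. T1 is a post-randomisation visit under open-label allocation, and the protocol calls it baseline for CT. The 6-minute walk and accelerometer have no value before allocation, and the only MFI before allocation is preoperative. The Section 8 covariates omit every pre-randomisation fatigue score, although the T0.1 MFI is scheduled and the NRS is obtained for eligibility.

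The primary comparison is unaffected. Secondary longitudinal or change results could be biased if T1 is used as their reference and knowledge of allocation shifts T1 scores. Neither condition is established by the documents, and the size and direction cannot be derived from them.

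The conflict over the timing of written consent is a separate, plain contradiction. It adds nothing to the argument about bias.

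**What to change.** 1. In Section 8, add T0.1 MFI-General Fatigue and the discharge NRS to the covariates of the adjusted analysis. This needs no extra visit or form, only that the NRS value itself is recorded and kept.
2. In Sections 6.1.2 and 6.3, call T1 a post-randomisation, pre-programme visit rather than baseline, and state in Section 8.2 that it is a post-randomisation time point. For the 6-minute walk and accelerometer, say that no pre-allocation value exists. This is a change of wording only.
3. In Appendix 2, add one MFI at T0.2, completed before the allocation is released. The cost is one 20-item form for patients about to leave hospital.
4. Separately, reconcile Section 9.2 with Appendix 2 so that no T0.1 study measurement precedes written consent. This is a change of text, plus a check of the consent procedure at each centre.

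### Section 6.2 publishes block sizes that can only be 2 and 4 within centre-by-organ strata of an open-label trial, making the next allocation often guessable while the discharge NRS gate is still open

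*Protocol*

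**What the plan says.** Protocol 6.2 makes the randomisation central: "Centralized stratified permuted block randomization will be performed by the Clinical Trial Center using the online ALEA software". Eligible patients enter when the discharge score qualifies ("If at hospital discharge patients score ≥ 4 on the fatigue NRS"), and "they will randomly be assigned to the treatment (rehabilitation program) or control (standard care) group in a 1:1 ratio". On strata, "The sample will be stratified based on organ (liver, pancreas, biliary tract) and organisation (EMC, LUMC, AMC, UMCG", which makes 3 x 4 = 12. On blocks, "Block randomisation within each stratum will be performed using variable block sizes ranging from 2 to 4". On blinding, "Neither patients nor therapists will be blinded for the treatment group". The only people said to be blinded to arm are those reading the CT measures (6.1.2).

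On consent the document gives two accounts. Section 9.2 says that "with hospital discharge patients will be asked to give written informed consent. Randomization will then be performed". Appendix 2 marks informed consent once, in the screening column. The protocol does not say who scores the NRS, who requests the allocation, or whether that person has seen earlier allocations.

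**The concern.** Central software hides the allocation list. It does not hide the pattern from anyone who knows the block sizes and has seen earlier open-label assignments in the same stratum. Because centre is a stratification factor, each of the 12 sequences lies entirely within one hospital, and the sizes are printed in the protocol that hospital holds. The smaller the blocks, the sooner each sequence must return to balance and the easier the next arm is to guess.

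This matters only if some discretion remains when the guess can be made. Here it does: eligibility turns on a fatigue score taken at discharge, just before randomisation. A person who expects one arm could, without intending to, treat a borderline score or a hesitant patient differently from when expecting the other. The result would be selection bias in an open-label trial whose primary outcome, MFI-General Fatigue, is self-reported. It is hard to remove afterwards. The adjustment covariates in section 8 are gender, age, education, marital status, disease stage and radicality of resection, and none of them captures the patient's state at discharge.

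**Working it through.** The protocol gives no figure for predictability, so there is none to reproduce.

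**Inputs.** Ratio 1:1, 12 strata and block sizes from 2 to 4 (6.2). A block of 3 cannot be balanced at 1:1, which leaves 2 and 4. Total of 154 patients, and 64 per group before dropout (2.4). Organ mix of 120 liver, 150 pancreatic and 30 bile duct operations (2.1), that is 40%, 50% and 10% of 300. Assumptions: centres recruit equally, enrolment follows the surgical mix, sizes within a set are equally likely, and the observer knows the sizes and every earlier allocation in the stratum.

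**Stratum sizes.** 154 x 0.40 / 4 = 15.4 liver; 154 x 0.50 / 4 = 19.25 pancreas; 154 x 0.10 / 4 = 3.85 biliary. I use 15, 19 and 4.

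**How the guess arises.** The first patient is a coin toss. The second is guessed as the opposite arm, which is right with probability 0.5 x 1 + 0.5 x 2/3 = 0.833. If the first two share an arm (probability 0.5 x 1/3 = 0.167), the block must be a 4, so patients 3 and 4 are known with certainty. Overall, the fourth patient is guessed correctly with probability 0.917.

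**Whole strata.** Exact Bayesian updating of the observer's belief, patient by patient, weighted over strata of 4, 15 and 19 (simulation for the 4, 6, 8 row):

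| Block sizes | Correct guesses | Certain allocations |
|---|---|---|
| 2 and 4 (plan) | 70.8% | 9.6% to 10.0% |
| 4 and 6 | 67.5% | 5.3% to 5.4% |
| 4, 6 and 8 | about 66% | about 2% |

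The lower ends of the ranges are exact; the upper ends come from a separate simulation. Chance is 50%. In a stratum of 13, the simple rule of guessing the arm that is behind does as well as the full calculation (70.4% for both). If the 2:4 mix is 25:75 or 75:25 instead of equal, correct guesses in a stratum of 13 run from 69.6% to 71.5% and certain allocations from 13.1% to 5.8%. With 4, 6 and 8, the second patient is guessed correctly with probability (2/3 + 3/5 + 4/7)/3 = 0.613.

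**Possible bias.** Suppose the recruiter shifts prognosis by +/-eta SD according to the guess, and guesses correctly with probability p. The mean shift is eta(2p - 1) in one arm and the opposite in the other, so the arm difference is 2 x eta x (2p - 1). The documents give no eta, so I show a range.

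| eta (SD) | Blocks 2 and 4 (p = 0.708) | Blocks 4, 6, 8 (p = 0.66) |
|---|---|---|
| 0.02 | 2 x 0.02 x 0.416 = 0.017 | 0.013 |
| 0.10 | 0.083 | 0.064 |
| 0.20 | 0.166 | 0.128 |

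With 64 per group the standardised shift is the difference x sqrt(64/2). Under a normal approximation, 0.017, 0.083 and 0.166 SD would turn a nominal 5% two-sided test into about 5.1%, 7.6% and 16%.

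**Cost in balance.** Mean absolute imbalance over all 12 strata is about 2.3 patients for 2 and 4, 2.7 to 2.8 for 4 and 6, and 3.1 for 4, 6 and 8. For a biliary stratum of 4, the chance of a 3:1 or worse split is:
- 2 and 4: 0.5 x 0.5 x 1/3 = 0.083
- 4 and 6: 0.5 x (1 - 9/15) = 0.20
- 4, 6 and 8: (0 + 6/15 + 34/70)/3 = 0.295

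**The case against.** The best defence is that allocation is already central with varying blocks, and that small blocks are a reasonable choice for 12 small strata. The gain from larger blocks is also modest: correct guesses fall by about 5 points and the induced difference by 0.004 to 0.04 SD over the range of eta, against a design effect of 0.50 SD. All of this stands. The stronger gains are fewer certain allocations (about 10% to about 2%) and not handing the sizes to sites at all.

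Several stronger readings are tempting, but the document does not support them.

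- A reader might infer that recruiters do see every earlier allocation. The protocol does not say so, and exercise is delivered close to the patient's home and psychotherapy at home (6.3), not on the discharging ward. The 71% is therefore an upper figure, for one fully informed observer.
- A reader might infer that consent is still open when the guess can be made. That follows from 9.2, but Appendix 2 puts consent at screening and 6.2 has patients included preoperatively. The discharge NRS gate is open on either reading.
- A reader might infer that motivation goes unmeasured before allocation. MFI-Reduced Motivation is measured preoperatively (section 1, Appendix 2). It is not the same as willingness to enter rehabilitation, and section 8 does not list it as a covariate, but it is measured.
- A reader might take the absence of an NRS row in Appendix 2 to mean that the score could follow allocation. Sections 6.2 and 9.2 already place the score and consent before randomisation, so locking those entries would add little.

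**Conclusion.** The point holds in a limited form. Section 6.2 discloses a scheme that can only be blocks of 2 and 4 inside single-centre strata of an open-label trial. An informed observer would guess the next arm about 71% of the time, rising to 83% for the second and 92% for the fourth patient in a stratum, and would be certain for about 10%. These figures rest on equal weights for the two sizes, equal centres, and sight of earlier allocations, which is inferred.

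The consequence for the primary comparison cannot be read from the document. Assumed selection shifts of 0.02 to 0.2 SD give about 0.02 to 0.17 SD, so the effect could be negligible or could be a third of the design effect (0.166 / 0.50 = 0.33). The document does not show that concealment has failed. It shows an avoidable weakness that is cheap to close before enrolment and hard to repair in the analysis.

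**What to change.** In 6.2, remove the block sizes from the site-facing text and state that randomly varying block sizes, with no blocks of 2, are set and held by the Clinical Trial Center and not disclosed to sites. Sets such as 4 and 6, or 4, 6 and 8, would serve, recorded in a document the sites do not hold. Withholding the sizes is the essential part, because larger sizes alone cut guessing only modestly while centre remains a stratification factor.

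Separately, reconcile 9.2 with Appendix 2 on when consent is given.

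The cost is one sentence and a setting in the randomisation software, plus somewhat more imbalance. On average this is under one more patient overall (about 2.3 to 3.1 with 4, 6 and 8). In biliary strata of 4, splits of 3:1 or worse rise from about 8% to about 20% (4 and 6) or 29% to 30% (4, 6 and 8). If balance in the biliary strata matters most, 4 and 6 is the milder choice.
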